**SCHEMA 2: Healthy subjects**

List of Abbreviations and definitions of terms

aGVHD	Acute Graft versus host disease
BMT	Bone marrow transplant
CD4	Cluster of differentiation 4
CD8	Cluster of differentiation 8
CDA	Cytidine deaminase
[¹⁸ F]-CFA	[¹⁸ F]Clofarabine; 2-chloro-2'-deoxy-2'-[(¹⁸ F)fluoro-9-β-D-arabinofuranosyl-adenine
CMC	Chemistry, Manufacturing and Controls
dCK	Deoxycytidine kinase
dGK	Deoxyguanosine kinase
[2]-F-D-AraC	1-(2'-deoxy-2'-[¹⁸ F]fluoro-β-D-arabinofuranosyl)cytosine
[¹⁸ F]F-AraG	2'-deoxy-2'-[¹⁸ F]fluoro-9-β-D-arabinofuranosyl guanine
F-18, ¹⁸ F	Fluorine 18
GI	Gastrointestinal
HCT	Hematopoietic cell transplant
HLA	Human Leukocyte Antigen
F-18, ¹⁸ F	Fluorine 18
FDA	Food and Drug Administration
FDG	2-deoxy-2-(¹⁸ F)fluoro-D-glucose
IND	Investigational new drug
IRB	Institutional Review Board
IV	Intravenous
MRI	Magnetic resonance imaging
PET/CT	Positron emission tomography – computed tomography
SUV	Standardized Uptake Value
ROI	Region of interest
IHC	Immunohistochemistry
SUV	Standard uptake value

1. OBJECTIVES

We have developed a Fluorine-18 PET tracer 2'-deoxy-2'-[18F]fluoro-9-β-D-arabinofuranosyl guanine ([¹⁸F]F-AraG), based on a drug called AraG that is known to be selective towards T cells. Our initial findings with this tracer have shown similar mechanism(s) of uptake as AraG and preferential accumulation in activated T cells. The selected positron emission tomography (PET) tracer ([¹⁸F]F-AraG has shown promise in preclinical studies in a mouse model of acute Graft versus Host Disease (aGVHD). We have shown the ability to use [¹⁸F]F-AraG PET imaging to quantitatively visualize locations of T cell accumulation during and early late-stage GVHD in this model. Moreover the tracer has already undergone the first in human studies in healthy human volunteers where it showed a favorable biodistribution, clearance profile and *in vivo* stability. With promising preclinical and clinical data, the tracer warrants further characterization in aGVHD patients where there is a pressing and unmet need for early detection of the disease. We hypothesize that *in vivo* molecular imaging can be safely utilized to identify sites of GVHD and therefore propose the following specific aims:

1.1. Primary objective

Evaluate the feasibility of [¹⁸F]F-AraG PET/CT scanning in patients with graft versus host disease

We hope to determine whether [¹⁸F]F-AraG, demonstrates good uptake in regions of GVHD as confirmed by GI biopsy. The performance of [¹⁸F]F-AraG PET/CT will be assessed on a per-lesion based analysis in a cohort of up to 25 GVHD patients. The tracer's biodistribution, and dosimetry will be studied in all aGVHD patients. All critical data shall be reported to the FDA.

The ultimate goal of this study is to investigate the predictive power of [¹⁸F]F-AraG and whether it can be used to diagnose GVHD at its earliest stages to allow for more timely treatments to be applied in the future, to monitor treatment efficacy, and to hopefully improve the outcome of patient's with this devastating and frequent complication of allogeneic hematopoietic cell transplantation.

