2.6 Study Design

Study participants will consist of healthy volunteers for extended studies on radiotracer behavior and patients belonging to a GVHD group. Two patient categories exist within the GVHD group-those highly suspected to have acute GVHD and those that are at high risk for developing acute GVHD. We will recruit healthy volunteers through local advertising. We will recruit high risk and confirmed GvHD patients from the Bone Marrow and Transplantation Clinic at the Stanford Cancer Institute.

Normal subjects will be recruited by publicly disseminating the information about the clinical trial through printed media such as a flyer, or by sending out an email to the Stanford community. We will ask for volunteers. A consent form for healthy volunteers is also included. Patients will undergo preliminary evaluation to ensure eligibility, receive and sign an informed consent, be enrolled in the trial, and then have [¹⁸F]F-AraG PET/CT.

Highly suspected acute GVHD patients will be scanned following biopsy (taken to confirm acute GVHD). The staging and grading of the disease using the Glucksberg grade and International bone marrow Transplant Registry Severity Index (IBMTR) at time of enrollment will be noted. Their consent for a PET-CT scan will be obtained prior to biopsy. Biopsy tissues of consented patients will be analyzed further for T cell involvement.

High-risk patients (recipients of myeloablative or reduced intensity allogeneic transplants using either bone marrow or peripheral blood stem cells from HLA-matched or HLA-mismatched related or unrelated donors-protocols 9917, 9142, 9022, 9924) will have to sign consent forms

before they undergo a transplant. All those that consent will undergo a PET-CT scan day 4 \pm 2 days post transplant. Additionally these patients will be scanned again between day 14-21 post transplant. Follow up on these patients will note those that go on to develop aGVHD and the clinical end point will be correlated to the scans to verify any predictive potential of the radiotracer.

For both GVHD groups-results of the scan will be compared to biopsy results and immunohistochemical staining of the biopsy samples for T cells.

Investigational agent: $[^{18}\text{F}]\text{F-AraG}$ will be formulated in a sterile and pyrogen-free isotonic solution will be administered in a single slow IV injection.

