3 PARTICIPANT SELECTION AND ENROLLMENT PROCEDURES

3.1 Inclusion Criteria

This study will enroll three cohorts of participants: healthy volunteers, patients highly suspected to have acute GVHD and requiring systemic therapy, and patients at high risk for developing acute GVHD. For patients highly suspected to have acute GVHD and requiring systemic therapy, biopsy of involved tissue is encouraged to support the clinical diagnosis- this will normally be taken from the gastrointestinal tract. T cell staining will be incorporated in the immunohistochemical analysis of the tissue.

Participants must meet all of the following relevant criteria to participate:

1. Must be 21 years of age or older.
2. Must understand and voluntarily have signed an Informed Consent after its contents have been fully explained.
 - a. For patients highly suspected to have acute GVHD and requiring systemic therapy, informed consent should be signed prior to biopsy taken to support clinical diagnosis.
 - b. For patients at high risk for developing acute GVHD, informed consent should be signed prior to transplant.
3. For healthy volunteers only: Must have no known medical problems that would make undergoing the scan hazardous to the health of the patient or interfere with the results. In particular subjects should not have any cardiac or immunological disorders as these would likely affect the scan results. Subjects should have had a full physical exam within 6 months of the study. If healthy volunteers have not had a full medical exam within 6 months of the study, one of the nuclear medicine physicians will conduct the medical exam prior to any study procedures.
4. For patients highly suspected to have acute GVHD and requiring systemic therapy only:

Taking steroid treatment for suspected acute GVHD for 7 days or less.

5. For patients at high risk for developing acute GVHD only: Recipients of myeloablative or reduced intensity allogeneic transplants using either bone marrow or peripheral blood stem cells from HLA-matched or HLA-mismatched related or unrelated donors (protocols 9917, 9142, 9022, 9924) who have not yet been placed on any therapy for acute GVHD.

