10.5 Analysis

10.5.1 Analysis Population

Analysis population: all ROIs drawn on various organs, as well as areas with elevated SUV relative to healthy volunteers.

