10.5.2 Analysis Plan

Although the study will have low power due to the constrained sample size, in addition to descriptive statistics we will perform the following statistical analyses:

- In the highly suspected group:
Spearman rank correlation between median or maximum SUV values across ROIs and disease severity
- In the high-risk group:
Spearman rank correlation between SUV values in the first and second scans prediction of disease status at end of follow-up (aGVHD or no aGVHD) from SUV values of the first and second scans (using logistic regression)

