10.6 Secondary Analysis

10.6.1 Analysis Population

Analysis population: biopsy samples from the high suspected aGVHD group, as well as any later performed on the high-risk aGVHD group.

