10.6.2 Analysis Plan

Although the study will have low power due to the constrained sample size, in addition to descriptive statistics we will perform Spearman rank correlation between the SUV values and IHC measurements in biopsy locations.

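### The primary objective promises a per-lesion assessment against GI biopsy in up to 25 GVHD patients, but no primary analysis is specified per lesion or uses biopsy; patient pharmacokinetics are promised without timed sampling

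*Combined protocol and SAP*

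**What the plan says.** **Objective.** Section 1.1 sets feasibility as the primary objective. It asks whether uptake is good in GVHD regions confirmed by GI biopsy, and says performance "will be assessed on a per-lesion based analysis in a cohort of up to 25 GVHD patients". It adds that dosimetry will be studied in all aGVHD patients. Section 1.2 adds pharmacokinetics in GVHD patients.

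**Primary analysis.** The population in 10.5.1 is "all ROIs drawn on various organs, as well as areas with elevated SUV relative to healthy volunteers". Besides descriptive statistics, 10.5.2 lists for the highly suspected group (Arm 1) a "Spearman rank correlation between median or maximum SUV values across ROIs and disease severity". For the high-risk group (Arm 2) it lists a Spearman correlation between the two scans and a logistic regression of later aGVHD on SUV.

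**Biopsy.** Section 2.6 says that in both GVHD groups "results of the scan will be compared to biopsy results and immunohistochemical staining of the biopsy samples for T cells". In section 10 this appears only as the secondary analysis, a "Spearman rank correlation between the SUV values and IHC measurements in biopsy locations" (10.6.2), in a population of "biopsy samples from the high suspected aGVHD group, as well as any later performed on the high-risk aGVHD group" (10.6.1). On availability, 2.6 says "Highly suspected acute GVHD patients will be scanned following biopsy (taken to confirm acute GVHD", whereas in 3.1 "biopsy of involved tissue is encouraged to support the clinical diagnosis".

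**Kinetics.** Section 9.2 names kinetic behavior as an outcome for healthy subjects only.

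**The concern.** An objective fixes a unit of analysis, a reference standard and a cohort. Section 1.1 fixes all three, and the primary analysis in section 10 takes up none of them. It works with SUV summaries, severity grades and later disease status. A team that followed section 10 exactly could complete the primary analysis without tabulating uptake at the sites biopsy had confirmed.

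This also affects a decision. Section 10.8 has up to 10 Arm 1 patients scanned, and the scans examined for whether the tracer images the disease, before Arm 2 opens. No lesion-level summary is specified for that look.

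The pharmacokinetic promise in 1.2 has the same weakness: it is a stated objective for which the patient schedule collects almost no suitable data.

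**Working it through.** The documents give no alpha, power or effect size, so there is no sample-size figure to reproduce. The check sets objectives against outcomes, analyses and schedules.

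**1. Objective against primary analysis (1.1 against 10.5.2)**
- Arm 1, SUV against severity: the ROIs are reduced to a median or maximum. Not per lesion, no biopsy.
- Arm 2, scan against scan: unit not stated, no biopsy.
- Arm 2, logistic regression: the outcome is one value per patient, no biopsy.

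Result: 0 of 3 specified per lesion, 0 of 3 referenced to biopsy. Section 9.1 agrees with 10.5.2 rather than 1.1: its primary outcomes are clinical severity or development of aGVHD, and IHC is secondary. Section 8.2 records SUV and volume for each ROI and 10.5.2 includes descriptive statistics, but nothing ties an ROI to a biopsied site.

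**2. Who can contribute a biopsy-confirmed site**
- Section 10.7: up to 25 GVHD patients, roughly half per arm. 25 / 2 = 12.5, so about 12-13 per arm. This is a rough split, not a ceiling.
- Arm 2 patients consent before transplant and are not yet on aGVHD therapy (3.1). They contribute only if biopsied later.
- In Arm 1, 2.6 reads as if every patient has a biopsy; 3.1 only encourages one.

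The base is therefore the biopsied Arm 1 patients plus any biopsied Arm 2 patients. It equals 25 only if everyone is biopsied.

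**3. Scan-to-biopsy timing**
- Arm 1: under 2.6 and 3.1, consent precedes biopsy. If consent falls in the screening window of Table 6-2 (Day -30 to Day 1), the gap is about 30 days at most. Appendix A puts consent after biopsy, which removes that bound.
- Arm 2: a biopsy found in follow-up can come up to 6 months after the final scan (9.1.2).

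The secondary correlation pools these pairs.

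**4. Several sites per patient (illustration only)**
The documents give neither the number of sites per patient nor the intraclass correlation (ICC). Suppose there is no true association, m sites per patient, and the same ICC in SUV and IHC. The variance of a correlation computed as if sites were independent is then inflated by about V = 1 + (m - 1) x ICC². A nominal two-sided 5% test rejects with probability of about 2 x [1 - Φ(1.96/√V)]. For ICC 0.3 / 0.5 / 0.7:
- m = 1: V = 1, so 5%.
- m = 2: V = 1.09 / 1.25 / 1.49, so 6.0 / 8.0 / 10.8%.
- m = 3: V = 1.18 / 1.50 / 1.98, so 7.1 / 11.0 / 16.4%.

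Simulation with 12 patients (20,000 trials) gave 5.2 / 5.4 / 5.3%, 5.8 / 7.4 / 10.7% and 6.8 / 10.3 / 16.2%. If only one variable clusters there is no inflation (about 5%).

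**5. Kinetics (1.2 against 5.1, 6 and 9)**
- Timed tracer blood samples: healthy subjects 10 (one before injection, nine from 1 to 90 minutes); GVHD patients 0. Patients have a pre-injection safety sample and one at follow-up on day 2-7.
- Dynamic scan: 30 minutes in healthy subjects, none in GVHD patients.
- Static scan times per GVHD session: one required (60 minutes), one more if tolerated (30 minutes).
- Section 5.1 step 6 lets patients' catheters be used for blood collection, and 9.1.1 describes plasma assays without naming a cohort. Neither schedules a sample.

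**The case against.** The strongest reply is that this is a pilot. Its headline objective is feasibility, 10.7 says the sample is too small for formal tests, and the plan is not silent: descriptive statistics cover all ROIs, including gut regions (9.1.1), and 10.6.2 works at biopsy locations. Much of this stands, and it rules out several stronger readings.

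- A reader might infer that the plan has no biopsy-referenced analysis or no regional SUV summary. It has both. What is missing is a primary summary linking regions to biopsied sites.
- A reader might take the rejection rates above as a defect in a test the trial relies on. Section 10.6.2 states no alpha or decision rule, and no passage says that patients contribute several sites. With one site each there is no inflation.
- A reader might treat 12-13 as a maximum for Arm 1. Section 10.7 says only roughly half, and 10.8 gives Arm 1 priority. Nor can the incidence figures in 2.1 bound the number biopsied: they concern GVHD overall rather than GI disease, and the upper one is open-ended.
- A reader might conclude that nothing kinetic can be seen in patients. Scans at 30 and 60 minutes would allow a sparse, image-based description of uptake.

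The pilot argument does not remove the core, because a descriptive table needs no power. Rewording 1.1 alone would restore consistency, but would leave the look in 10.8 without a lesion-level summary.

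**Conclusion.** The mismatch is real and wrong as written. The primary objective names a per-lesion, biopsy-confirmed assessment in up to 25 patients; 0 of 3 primary analyses is specified that way, and the biopsy-referenced base is the biopsied patients only. The secondary objective promises patient pharmacokinetics with 0 timed tracer samples and no dynamic scan, so the schedule supports at most sparse image-based uptake. These statements come directly from the text and need no assumption.

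Two parts are conditional. The 30-day limit on the Arm 1 interval assumes that consent precedes biopsy and falls within the screening window. The effect of clustering depends on an unknown number of sites and ICC, and ranges from none to about 16% in the cases shown; it is a reason to specify the unit of inference, not a measured error. This should be corrected before analysis, and the Arm 1 summary before the look in 10.8.

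**What to change.** 1. In 10.5, beside the existing analyses, add a primary descriptive summary of SUV at biopsied sites by histology result in Arm 1, stating the numbers of patients and sites. Use the same summary for the Arm 1 look in 10.8.
2. In 10.6, report Arm 2 biopsies separately, each with the nearest scan, and give the scan-to-biopsy interval. If any patient contributes more than one site, keep the site-level description but base any interval or p-value on the patient as the cluster. In simulation with 12 patients and three sites each, a patient-level permutation test rejected in 4.5-5.3% of trials and a patient-level bootstrap in 6.9-7.4%.
3. In 1.1, restate the per-lesion cohort as GVHD patients with a biopsy: Arm 1, roughly half of up to 25, plus any biopsied Arm 2 patients reported separately. Set no fixed ceiling.
4. In 1.2, limit GVHD patients to biodistribution, toxicity and descriptive uptake at the imaged times. Leave blood-based kinetics to the healthy cohort, as in 9.2, and say in 9.1.1 that the plasma assays apply to that cohort. State the basis of any patient dosimetry.
5. Reconcile 2.6 and 3.1 with Appendix A on whether consent comes before or after biopsy, and 2.6 with 3.1 on whether all Arm 1 patients have one.

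Cost: the work of matching biopsy sites to PET regions, a protocol modification under 8.1, and narrower stated objectives. No extra scan, biopsy or patient is needed.

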1.2. Secondary Objectives

The tracer's pharmacokinetics, biodistribution, dosimetry and toxicity will also be studied in GVHD patients having been previously studied in healthy volunteers. Further, extended characterization of tracer biodistribution will be carried out in a small number of healthy subjects.

2. BACKGROUND

2.1. Acute Graft versus Host Disease

Allogeneic hematopoietic cell transplantation (HCT) is an increasingly used curative option for many hematological malignancies, and other life-threatening genetic and hematological diseases [3, 4]. HCT is capable of destroying residual tumor cells that persist after radiation treatment or chemotherapy, an effect called the graft-versus-tumor reaction. However, the main complications of HCT are infections and acute graft-versus-host disease (aGVHD). Whilst infections can be treated successfully, patients with aGVHD by the time of diagnosis are less responsive to treatments. Thus a principle challenge for more successful implementation of HCT has been avoidance or better management of aGVHD. Whilst considerable medical advancements have been made in the last two decades, the diagnosis and treatment of this devastating disease has only marginally improved during that time.

This immunological disorder arises when donor T cells react to “foreign” host human leukocyte antigens (HLA), causing a wide spectrum of host tissue injuries in the gastrointestinal (GI) tract, liver, skin, and lungs [3, 5]. Two phases of the disease have been described; first the migration of CD4+ and CD8+ donor T cells to secondary lymphoid organs where they are activated by innate immune cells that become reactive by the conditioning therapy for HCT[6]. The second phase is characterized by massive proliferation of these alloreactive T cells which then home to various organs (GI tract, liver and skin are tissues that are commonly affected) and start to attack host cells via direct cytolysis or by cytokine production causing a wide range of symptoms [3].

Incidence rates of GVHD are high and depend on the degree of HLA histocompatibility, the prophylactic regimen used, patient age, and the number of T cells in the graft [5]. GVHD can affect 20-50% of patients receiving related donor transplants [7-10] and upwards of 70% of patients receiving HLA-matched unrelated donor transplants [7, 10]. The overall grade of GVHD is known to have a major effect on patient outcome, with grade I or II cases associated with little morbidity and no mortality, and grade IV cases associated with close to 100% mortality [5]. Hence, GVHD is a leading cause of morbidity and mortality of HCT therapy and improved ways of managing this complication could lead to more widespread use of this effective therapeutic paradigm for hematological malignancies, autoimmune diseases, or organ transplant rejection [11, 12]. Since long term survival of grade III-IV aGVHD is a dismal 10-20% [13], it is important to detect patients who will progress to high-grade aGVHD earlier in their course.

Unfortunately, early definitive GVHD diagnosis is often difficult due to its non-specific symptoms and numerous differential diagnoses (e.g., drug toxicity, infections, and side effects from conditioning regimen) [14, 15]. GVHD is typically diagnosed at late stages when overt symptoms such as skin, GI, or liver problems become apparent, and is often one of exclusion, delaying the onset and effectiveness of potentially life-saving prophylactic interventions [16, 17]. Moreover, invasive endoscopic guided biopsy (often from liver or GI tract) and subsequent histology are still the state-of-the-art way to confirm a GVHD diagnosis [7]. These can be challenging to perform due to bleeding and critical illness associated with HCT. Dramatic differences in estimated response rate at a particular disease stage have been reported including 63% to 95% for grade II, 17% to 30% for grade III, and 0% to 6% for grade IV patients [18]. The severity of GVHD is also difficult to quantify, with staging relying on the assessment of the clinical changes seen in the skin, GI tract, liver, and performance status [5, 16, 17]. Therefore, **non-invasive methods that can effectively track alloreactive donor T cell dynamics, stratify the risk of aGVHD prior to overt symptoms and thus diagnose GVHD at earlier stages are urgently needed but entirely lacking.**

Present day clinical management

Several imaging techniques have shown promise for definitive diagnosis of GVHD, particularly GI manifestations of the disease, including magnetic resonance imaging (MRI), computed tomography (CT), high-resolution transabdominal ultrasound and color Doppler ultrasound [19, 20]. These techniques primarily focus on structural manifestations such as detection of edema and thickening of the intestinal wall that become apparent during advanced stages of GVHD, and are therefore likely limited for early disease detection. Molecular imaging of aGVHD, which could yield a more sensitive detection, has been very limited focusing mostly on PET imaging using [¹⁸F]FDG [21].

[¹⁸F]FDG PET has shown promise for imaging intestinal inflammation associated with GVHD in both mouse models and patients with early clinical symptoms, even allowing prediction and

monitoring of therapy response in these patients [21]. However, the utility of [¹⁸F]FDG PET imaging for early detection prior to clinical symptoms is not known and the non-specific nature of [¹⁸F]FDG imaging for a variety of activated immune cell types should enable a selective advantage of [¹⁸F]F-AraG PET imaging for this purpose.

Numerous candidate blood biomarkers are also under active investigation including soluble CD30 [22], regenerating islet-derived 3-alpha (REG3a) [23], microRNAs [24], amongst others [25, 26]. de Bock et al have also recently identified variations in a panel of proteomic blood biomarkers approximately 15 days before definitive GVHD diagnosis [27]. These candidates however require further validation prior to widespread clinical use and thus to date not a single biomarker has been approved for early aGVHD diagnosis [27-29]. Cellular blood biomarkers of GVHD have also been explored. Bauerlein et al. have shown that, during their migration to effector organs, peripheral blood detection of alloreactive T cells expressing homing receptors (a4b7 integrin and P-selectin ligand) can be used to define a diagnostic window for the improved treatment of GVHD [28]. Notably, if immunosuppressive (i.e., Rapamycin) treatment is administered at the time of earliest alloreactive T cell detection then progression to lethal GVHD was prevented [28]. We believe that whole body [¹⁸F]F-AraG PET imaging that can quantify activated T cell accumulation during the initiation phase may provide a highly complimentary technique to these *in vitro* diagnostics to provide more definitive GVHD diagnosis and with spatial information. Hypothetically, it may even enable earlier diagnosis than a blood-based strategy by detection of T cells in priming sites prior to migration of cells or shedding of cellular proteins into the peripheral blood. Overall the continued evaluation of [¹⁸F]F-AraG PET imaging for GVHD diagnosis and treatment monitoring could enable this technology to fulfill a critical need in the management of this terrible disease to allow more widespread success of HCT therapy.

